7.1.5. Statistical Analyses / Methods

Details of the planned displays are provided in [Appendix 11: List of Data Displays](#) and will be based on GSK data standards and statistical principles.

Unless otherwise specified, endpoints / variables defined in Section [7.1.1](#) will be summarised using descriptive statistics, graphically presented (where appropriate) and listed.

7.1.5.1. Statistical Methodology Specification

Endpoint / Variables																		

 BAL total protein at 26h (LPS lobe). It is anticipated that pharmacodynamic and biomarker endpoints will require log_e-transformation in all analyses to improve the assumption of normality and hence improve model fitting. Following model fitting, back-transformation will occur and treatment effects (GSK2798745 relative to placebo) will be expressed as a percentage change. 																		
Model Specification																		

 The model described below is the default statistical model for BAL biomarkers with BAL samples taken at 2 h and 26 h. **analyte** in the text below should be replaced by the specific BAL endpoint in the analysis. The endpoint will be analysed using an analysis of covariance (ANCOVA) model fitted in a Bayesian framework with covariates having non-informative priors using PROC MCMC in SAS. The terms to be fitted in the model: 																		

  
 Type	Name	
   
 Dependent variable	• BAL **analyte** at 26 h (LPS lobe)	
 
 Fixed continuous independent variables	• Baseline (2 h) BAL **analyte**	
 
 Fixed categorical independent variables	• Treatment (GSK2798745, Placebo)	
  
		Type	Name	Dependent variable	• BAL **analyte** at 26 h (LPS lobe)	Fixed continuous independent variables	• Baseline (2 h) BAL **analyte**	Fixed categorical independent variables	• Treatment (GSK2798745, Placebo)									
Type	Name																	
Dependent variable	• BAL **analyte** at 26 h (LPS lobe)																	
Fixed continuous independent variables	• Baseline (2 h) BAL **analyte**																	
Fixed categorical independent variables	• Treatment (GSK2798745, Placebo)																	
Information on the effects and prior distributions for parameters:																		

  
 Type	Name (#Levels)	Parameters	Priors	
   
 Fixed Categorical	Intercept (1)	#1 Intercept	N(Mean= 0, Var=1E6)	
 
 Treatment (2)	#1 Placebo	N/a (constraint = 0)	
 
 #2 GSK2798745	N(Mean=0, Var=1E6)	
 
 Fixed Continuous	Baseline (2h) BAL **analyte**	Linear relationship between baseline (2 h) and 26 h LPS lobe BAL **analyte** (baseline slope).	N(Mean=0, Var=1E6)	
  
		Type	Name (#Levels)	Parameters	Priors	Fixed Categorical	Intercept (1)	#1 Intercept	N(Mean= 0, Var=1E6)	Treatment (2)	#1 Placebo	N/a (constraint = 0)	#2 GSK2798745	N(Mean=0, Var=1E6)	Fixed Continuous	Baseline (2h) BAL **analyte**	Linear relationship between baseline (2 h) and 26 h LPS lobe BAL **analyte** (baseline slope).	N(Mean=0, Var=1E6)
Type	Name (#Levels)	Parameters	Priors															
Fixed Categorical	Intercept (1)	#1 Intercept	N(Mean= 0, Var=1E6)															
	Treatment (2)	#1 Placebo	N/a (constraint = 0)															
		#2 GSK2798745	N(Mean=0, Var=1E6)															
Fixed Continuous	Baseline (2h) BAL **analyte**	Linear relationship between baseline (2 h) and 26 h LPS lobe BAL **analyte** (baseline slope).	N(Mean=0, Var=1E6)															

 The residual variance will be fitted with a non-informative inverse-gamma prior, $\text{igamma}(\text{shape}=0.0001, \text{scale}=0.0001)$. Any centering of variables is to occur after any transformation. Baseline (2h) BAL **analyte** is to be centered to improve mixing in PROC MCMC. An optional exploration/model building step may take place by adding other covariates to the model that may explain a significant proportion of variance in the response and/or imbalance between treatment groups at baseline and/or be justified by biological rationale/expert 																		

judgment or statistical tools (raw plots and model selection criteria). Only the results of the final model would be reported in the Clinical Study Report (CSR).

- For the final model, appropriate combinations of model parameters should be combined to obtain treatment effects of interest, including performing any back-transformations that are required. For example, assuming \log_e transformation is required, the percentage change in 26h BAL ****analyte**** will be obtained by computing $\exp(\beta_{GSK2798745})$ for each MCMC iteration, which should be programmed between the BEGINNODATA and ENDNODATA statements (within PROC MCMC procedure).
- To obtain probability statements for parameters/effects of interest use binary flag variables. For each MCMC iteration if the condition is satisfied the iteration is flagged as a 1, if not it is flagged as 0. The proportion of iterations flagged as 1 gives the posterior probability of the statement of interest i.e. the proportion of MCMC iterations for which the percentage reduction in BAL ****analyte**** for GSK2798745 c.f. placebo is greater than zero.
 - For example, the SAS syntax for computing the flag for any percentage reduction in BAL ****analyte**** would be: $flagsuccess = (ratio < 1)$; . Where *ratio* is the parameter used to store the ratio for adjusted posterior medians, GSK2798745 relative to placebo, calculated as $\exp(\beta_{GSK2798745})$, and *flagsuccess* being the binary success/fail flag.

Model Checking & Diagnostics

Ways to assess model appropriateness and fit can be assessed using a variety of tools. Some examples of methods are listed here:

- Use the DIC alongside expert judgment/biological rationale to select the most appropriate model. A difference in DIC between two models is >10 is generally considered substantial evidence of an important difference in model fit. Difference in DIC of <5 may be considered negligible.
- Examine trace plots for fixed parameters to evaluate whether there is constant mean and variance, that the chain is moving around the parameter space freely and moving rapidly between the extremes to show that the chain is stationary and mixing.
- Run at least 2 chains starting at different initial values. If all chains converge to the same point, then this is evidence of consistent convergence. Overlapping trace plots give visual reference for this. Running multiple chains is achieved by either by specifying initial values using *begincnst/endcnst* and using a *by* statement to run for each chain, or by using a macro to run PROC MCMC multiple times with initial values specified on the *parms* statement and different seeds specified for each run. Please consult GSK statistician for more details, including SAS syntax.
- The MCSE should be compared with the standard deviation of the posterior distribution (SD) to ensure that only a fraction of the posterior variability is due to simulation error. The ratio MCSE/SD should typically be ≤ 0.01 .
- Autocorrelation plots should be used to assess the correlation between each draw and its *k*th lag. The further the lag from the original measure the smaller you expect the correlation to be.
- Rather than using the prior distribution to generate starting values for parameters in the model, use raw plots or PROC MIXED (frequentist equivalent to Bayesian) parameter estimates to help determine starting values. This should help the model converge quicker and reduces the number of burn-in iterations required.
- Tailor the number of burn-in iterations, thinning, starting values, number of posterior samples

(10,000 minimum) to ensure satisfactory model fitting and diagnostic plots.

- As an optional check, use residual plots from the PROC MIXED (frequentist equivalent to Bayesian) model to examine model fit (relevant because non-informative priors are used in the analysis). Residuals should be normally distributed (assessed with a histogram or normal probability plot). Residuals and fitted values should be uncorrelated (assessed by plotting against each other and should appear random with no structure). Any pattern suggests that the model is not appropriate. The same plot can be used to examine if there is constant variance.

Model Results Presentation

- Point estimates (median values of posterior distributions), the standard deviation of the posterior distribution (SDs) and 95% credible intervals (CrI) intervals will be presented for each treatment group and treatment comparison (absolute and percentage change). A number of posterior probability statements will also be expressed, as described in [Table 2](#).

Table 2 Posterior Probability Statements of Interest

Posterior Probability Statement (where X = treatment ratio of GSK2798745 / Pbo)	Interpretation
PP ($X \leq 0.25$)	Posterior probability of at least a 75% reduction in mean BAL **analyte** GSK2798745 relative to placebo
PP ($X \leq 0.5$)	Posterior probability of at least a 50% reduction in mean BAL **analyte** GSK2798745 relative to placebo
PP ($X \leq 0.75$)	Posterior probability of at least a 25% reduction in mean BAL **analyte** GSK2798745 relative to placebo
PP ($X \leq 0.9$)	Posterior probability of at least a 10% reduction in mean BAL **analyte** GSK2798745 relative to placebo
PP ($X \leq 1$)	Posterior probability of any reduction in mean BAL **analyte** GSK2798745 relative to placebo
PP ($X > 1$)	Posterior probability of any increase in mean BAL **analyte** GSK2798745 relative to placebo
PP ($X > 1.1$)	Posterior probability of at least a 10% increase in mean BAL **analyte** GSK2798745 relative to placebo
PP ($X > 1.25$)	Posterior probability of at least a 25% increase in mean BAL **analyte** GSK2798745 relative to placebo
PP ($X > 1.5$)	Posterior probability of at least a 50% increase in mean BAL **analyte** GSK2798745 relative to placebo
PP ($X > 1.75$)	Posterior probability of at least a 75% increase in mean BAL **analyte** GSK2798745 relative to placebo

- Point estimates for each treatment group and treatment comparison (absolute and percentage change) will be expressed graphically. See [Appendix 11: List of Data Displays](#) for example displays.
- Plots of the posterior distributions for 26 h BAL ****analyte**** (back-transformed) will be presented for each treatment arm. In addition, the posterior distributions for the absolute difference and percentage change in 26 h BAL ****analyte**** for GSK2798745 relative to placebo will be presented.

Sensitivity and Supportive Analyses

- Sensitivity analysis 1: Assess whether there is a difference in baseline (2h) concentrations between treatment groups. The design of the study is such that baseline is observed 2 hours after the first dose of study treatment (see [Figure 1](#)). Thus, there is opportunity for inhibition of the TRPV4 channel and regulation of endothelial permeability before the baseline (2h) BAL is performed and instillation of LPS and saline challenges. Should there be a significant difference in baseline (2h) ****analyte**** between treatment arms this may be interpreted as initial concentrations (normal conditions) of ****analyte**** are being reduced. For example, '745 may reduce baseline BAL ****analyte**** for GSK2798745 c.f. placebo. This will be investigated through the use of a Bayesian ANOVA model with 2h ****analyte**** as the dependent variable and treatment group as the independent variable. See [Appendix 11: List of Data Displays](#) for further details.
- Sensitivity analysis 2: The primary analysis model may be fitted to include 26 h ****analyte**** (saline lobe) as a covariate. In a supportive analysis, the model will assess whether administration of saline in the contralateral lobe is associated with 26 h ****analyte**** in the lobe in which LPS and treatment are administered. If this is the case, then one explanation could be that the segmental LPS may have “spilled over” into other areas of the lungs including the saline lobe. This could also lead to a lower than anticipated LPS dose in the LPS lobe. The analysis would be supported by graphical displays of individual participants and their three lobe measurements (see [Appendix 11: List of Data Displays](#) for example displays). Secondly, a positive relationship between contralateral lobes could be interpreted as the BAL procedure resulting in some impact on the endothelial/epithelial lining i.e. the BAL procedure itself results in more irritation of the tissue and stimulates a biological response to a greater extent than anticipated and this results in increased permeability. Thus, by adjusting for 26 h BAL ****analyte**** (saline lobe) the model is partitioning any effect on BAL total protein due to the procedure and due to the LPS/study treatment. Another reason could be that saline impacts upon permeability. This list is not exhaustive and only speculates on the reasoning behind a significant impact in pulmonary edema in the saline lobe. Further clinical and biological expertise is required to draw any conclusions.
- Sensitivity analysis 3: A sensitivity analysis may be conducted to exclude participants for which their 26 h BAL ****analyte**** in the saline lobe increases by at least 40% relative to baseline. This is the 95th percentile of the credible interval for 11 participants that underwent segmental LPS challenge over 2 periods (measured at baseline and 26 h) at the Fraunhofer Institute, Germany [[Holz, 2015](#)]. The median for 26 h BAL total protein in the saline lobe was 13.7% (95% CrI - 8.8%, 40.4%). This sensitivity analysis is being conducted because some participants may have received a greater dose of LPS than anticipated, be more sensitive to the LPS dose, the BAL procedure may have been more invasive than anticipated, etc. This may confound any observed treatment effect.

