### 10.1. Sample Size Determination

The sample size of 30 participants per arm (1:1 allocation) is based on an upper limit of feasibility. [Figure 4](#) illustrates the probability of study success for a range of sample sizes and assumed true treatment effects unconditional on variability.

Assuming a true treatment effect of a 30% reduction in mean BAL total protein in participants receiving GSK2798745 relative to placebo at 24 h after segmental LPS challenge to the lung, the probability of study success for the study is 82% (this excludes the possibility of success from a review of secondary data), unconditional on the variability of BAL total protein in segmental LPS challenged lungs. Outright end of study success is defined as at least a 95% posterior probability that the percentage reduction in the mean 24 h post-LPS BAL total protein level (GSK2798745 relative to placebo) exceeds zero.

Despite limited historical information for guidance on the true treatment effect for GSK2798745, 30% is believed to be a rational estimate. However, probability of study success is sensitive to the true treatment effect – for example, the probability of study success reduces to 50% if the true treatment effect is 20% (GSK2798745 relative to placebo) with a sample size of 30 per arm but increases to 96% if the true treatment effect is 40%.

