3. PLANNED ANALYSES

3.1. Interim Analyses

The interim analyses will be undertaken by the study statistician and/or designates and the outputs will only be communicated to key members of the study team which may include the Project Physician Lead, Early Development Lead, Clinical Investigation Lead, Translational Biomarker Representative, Study Statistician, Project Statistician and Study Programmer(s). Following the decision made by this core group, the decision will be communicated to the wider study team. The decision will only be communicated to the site if the decision is made to stop.

The appropriate internal GSK procedures will be followed to ensure that access to unblinded participant level data is restricted to the relevant personnel performing the analysis. A secure directory will be created with restricted access for storage of data, programs, log files and outputs. Only participants contributing data towards the interim analysis will have their treatment codes unblinded as per GSK internal procedures.

Each interim analysis will be based on the predictive probability of meeting the end of study success criteria in the primary endpoint 26h BAL total protein (see [Figure 2](#) and [Table 1](#)). An interim analysis will take place once approximately 10 participants per arm have completed the treatment period to determine whether there is sufficient rationale to continue or discontinue the study. If the decision is made to continue then a second interim analysis will occur once approximately 20 participants per arm have been recruited. Sufficient participants will be recruited to obtain up to 30 evaluable participants per arm.

[figure not shown]
Recruitment into the study will continue whilst the interim analysis is taking place unless data emerges regarding concerns about safety and tolerability. Any communication to the site regarding interim analyses will only take place if a decision to stop the study is made. Should the study be stopped, all ongoing participants will complete their treatment period whilst no further participants will be recruited into the study.

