4.1. Protocol Deviations

Important protocol deviations (including deviations related to study inclusion/exclusion criteria, conduct of the trial, patient management or patient assessment) will be summarised and listed.

Important deviations which result in exclusion from the analysis population will also be summarised and listed. (Please refer to [Appendix 1](#): Protocol Deviation Management and Definitions for Evaluable Population).

Protocol deviations will be tracked by the study team throughout the conduct of the study in accordance with the Protocol Deviation Management Plan Version 1.0 (Dated: 18/JUN/2018).

- Data will be reviewed prior to unblinding and freezing the database to ensure all important deviations and deviations which may lead to exclusion from the analysis are captured and categorised on the protocol deviations dataset.
- This dataset will be the basis for the summaries and listings of protocol deviations.

A separate summary and listing of all inclusion/exclusion criteria deviations will also be provided. This summary will be based on data as recorded on the inclusion/exclusion page of the eCRF.

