5.4. Multiple Comparisons and Multiplicity

Due to the extensive use of a Bayesian framework and the early phase/exploratory nature of this study there will be no explicit multiplicity adjustments. Moreover, the decision framework for study success/fail is predetermined.

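### Covariates can be added to the primary model by staff who have seen treatment-group results, and only the final model is reported, so the stated 6% false-success rate is not assured

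*SAP*

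**What the plan says.** **The model.** The default in SAP 7.1.5.1 regresses 26 h BAL protein in the LPS lobe (log scale expected) on treatment and centred baseline. The section then allows more: "An optional exploration/model building step may take place by adding other covariates to the model". The grounds are variance explained, imbalance between arms at baseline, biological rationale or expert judgment, plots and selection criteria. It closes: "Only the results of the final model would be reported in the Clinical Study Report (CSR"). Protocol 10.3.1 gives the same open permission, and SAP 5.3.1 names age and gender only as examples.

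**The selection tool.** SAP 7.1.5.1 pairs DIC with expert judgment. It treats a difference above 10 as substantial and one below 5 as negligible, and sets no binding cut-off.

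**The displays.** In SAP Appendix 11, Table 2.2 (the primary results) has room for added covariates. Tables 2.3 and 2.4 cover the two saline-lobe questions. No table is reserved for the default ANCOVA.

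**The rule.** Protocol 10.1: "Outright end of study success is defined as at least a 95% posterior probability that the percentage reduction" is above zero. Protocol 10.3.4 and SAP 3.1 put the chance of success with an inactive drug at about 6%. SAP 5.4 makes no multiplicity adjustment and adds that "the decision framework for study success/fail is predetermined".

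**Who sees results.** Protocol 7.4 unblinds selected sponsor staff for the interims. SAP 3.1 says "the outputs will only be communicated to key members of the study team", a group that includes the study statistician. It restricts participant-level unblinded data to those running the analysis. Figure 2.2 (participant profiles by treatment group) and Listing 33 (BAL protein data) are interim deliverables. Under SAP 3.2 the final analysis follows distribution of the codes.

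**Exclusions.** SAP 4.1: "Data will be reviewed prior to unblinding and freezing the database to ensure all important deviations and deviations which may lead to exclusion" from analysis are captured.

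**The concern.** A success threshold has a known error rate only if the model behind it is fixed. SAP 5.4 calls the decision framework predetermined, yet nothing says which model feeds it once covariates may be added. The plan gives no date for the model-building step, and one of its listed grounds, imbalance between arms, needs treatment codes.

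At stake are the meaning of the trial's single success rule and the reader's ability to check it. If the default result is left out of the report, nobody can see whether the conclusion depended on the added covariates. That reporting gap exists however honestly the final model was chosen.

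**Working it through.** **Step 1. Reproduce the plan's figures.** Inputs are from Protocol 10.1: "The sample size of 30 participants per arm (1:1 allocation) is based on an upper limit of feasibility"; "Assuming a true treatment effect of a 30% reduction in mean BAL total protein"; log-scale variance 0.25 (SD 0.5), 95% interval 0.13 to 0.69; posterior probability at least 0.95, which under flat priors is a one-sided 5% test.

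- SE = 0.5 × √(2/30) = 0.1291.
- Smallest successful effect = 1 − exp(−1.645 × 0.1291) = 19.1% (plan: 19%).
- Success probability at a 30% reduction, variance fixed: Φ(0.3567/0.1291 − 1.645) = Φ(1.118) = 86.8%.
- The plan averages over variance uncertainty. A scaled inverse-chi-square distribution with 11 to 12 degrees of freedom (my choice, to match the stated interval) gives 81.9–82.3% (plan: 82%). At 20% and 40% reductions it gives 51.6–51.8% and 95.8–96.1% (plan: 50% and 96%).

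**Step 2. Reproduce the full design.** I simulated 6,000 trials with flat priors, a two-sample model on the log scale and the predictive-probability thresholds in SAP Table 1.

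- No effect: 2.68% succeed at the second interim and 3.40% at the final, total 6.1% (plan: about 6%).
- 30% effect: 58.55% + 24.05% = 82.6% succeed (plan: 83%). Stopping by 20 per arm: 1.03% + 58.55% + 1.55% = 61.1% (plan: 61%).

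**Step 3. Add model building.** Same design, no true effect, 8,000 trials per row. The default model was used at both interims and covariates were chosen only at the 30-per-arm readout. Each candidate model's posterior probability is P(t < −estimate/SE) on its residual degrees of freedom. DIC was approximated by AIC, which is close under flat priors. The number of covariates and their correlation with the outcome are assumptions; the documents give neither.

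| Covariates; correlation | Default | Lowest DIC | Most favourable within 5 DIC of best | Most favourable of all |
|---|---|---|---|---|
| 3; 0 | 5.9% | 6.1% | 7.0% | 7.0% |
| 3; 0.3 | 5.8% | 6.7% | 8.2% | 10.5% |
| 5; 0.3 | 6.0% | 6.9% | 8.5% | 15.1% |

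Monte Carlo SE is about 0.3 points. This run omits the baseline covariate and does not simulate a rebuild at an interim.

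**Step 4. Check with baseline in the model.** Fixed 30 per arm, 2 to 3 covariates, 6,000 null trials per setting: default 4.9–5.0%; lowest DIC 5.1–5.4%; adding only covariates imbalanced between arms 4.1–5.0%; most favourable of all 6.0–10.2%. A separate fixed-sample run gave 5.1–5.3% for the default, 4.6–5.9% by fit, 5.8–7.4% for the most favourable within 5 AIC points, and 7.9–10.9% for the most favourable of all.

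**Step 5. Exclusions.** SAP 4.1 places the deviation review before unblinding. SAP 3.1 unblinds the codes of everyone contributing to an interim. By the second interim that is about 2 × 20 = 40 of at most 60 participants.

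**The case against.** The step is optional, and this is a Phase 1 proof-of-mechanism study. A favourable treatment effect is not among the listed grounds. DIC differences below 5 are called negligible, which discourages idle additions. The saline-lobe covariate has its own table. The interim prediction in SAP 3.1 uses the default predictor, on the assumption that no covariates are added. Table 2.1, Figures 2.1 and 2.2 and Listing 33 are final deliverables, so the default ANCOVA could be refitted from the listed data. All of this stands and lowers the severity. It does not remove the gap: a reader should not have to refit the primary analysis, and treating close models as equivalent leaves the choice between them to judgment.

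Four stronger readings are tempting, and the documents do not support them:

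- *The 95% rule automatically loses its error rate.* Selection by fit, or adjustment for imbalance alone, barely moves it.
- *The whole core team sees participant-level unblinded data.* SAP 3.1 restricts that access, although the two interim displays named above do show individual data.
- *SAP 5.4 waives multiplicity because the decision is predetermined.* Its main reasons are the Bayesian framework and the early, exploratory phase; the predetermined framework is an added remark.
- *Nobody fixes who is Evaluable before an interim.* That can be said only of the SAP. The Protocol Deviation Management Plan, which governs exclusions, is not among the documents.

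**Conclusion.** The point holds in a limited form. The plan permits the primary model to be extended on open-ended grounds by staff who may have seen treatment-group results, and it does not require the default result to be reported. That the extension would come after unblinding is an inference: the SAP gives no timing, but the imbalance ground implies codes and nothing prevents it.

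The stated 6% is therefore not assured, rather than shown to be wrong. Under the assumed covariate sets, disciplined selection adds at most about one percentage point. A material rise needs a choice guided by the treatment effect; its size depends on the assumed number and strength of covariates. The reporting gap depends on none of these assumptions. The Evaluable-status question is secondary. This is a should-fix point.

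**What to change.** In SAP 7.1.5.1, state that the default ANCOVA (log 26 h protein on treatment and centred log baseline), or a covariate set named before the first interim unblinding, is the only model for the 0.95 and 0.75 decisions at both interims and the final. Delete the final-model-only sentence for the primary endpoint. Always report the default model, with any extended model beside it as a labelled sensitivity analysis. Align SAP 5.3.1 and the note to Table 2.2.

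Unless the Protocol Deviation Management Plan already does so, add that Evaluable status is fixed by blinded review before a participant's data enter an interim.

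The cost is wording. The small downside is that a useful covariate found later cannot drive the decision, though it can still be explored and reported.

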**Figure 4 Probability of Study Success (Unconditional on Variance) for a Range of Treatment Profiles and Sample Sizes**

[figure not shown]
Estimates for the mean and variance of BAL total protein in segmental LPS challenged lungs were obtained from data in an observational study assessing the variability of the inflammatory response to segmental LPS challenge by the Fraunhofer Institute of Toxicology and Experimental Medicine, Germany [Holz, 2015] using a random effects model with total protein levels from 11 participants measured at baseline and 24 h over 2 study periods. The data were assumed to be representative of future segmental-LPS challenged lungs to be observed in this study.

The estimate of the mean BAL protein in 24 h post-LPS challenged lungs on the  $\log_e$  scale is 5.47 (95% CI 5.23, 5.72). The variance estimate on the  $\log_e$  scale is 0.25 (95% CI 0.13, 0.69). A posterior distribution was formed for the standard deviation and for each possible value of standard deviation from this distribution the power of the study was calculated and multiplied by its probability. The resulting values were all summed to

give probability of study success unconditional on variance, which is a more accurate representation of the probability of study success rather than assuming a single variance estimate with no uncertainty.

Figure 5 shows the minimum observed treatment effect in the study that would achieve success (expressed as a percentage reduction in BAL total protein for GSK2798745 relative to placebo) for a number of sample sizes. Assuming the variance in the study is the median obtained from the historical data, the minimum treatment effect to trigger success is 19% for a sample size of 30 participants per arm. As the sample size increases, the minimum observed treatment effect that would trigger success decreases due to the decreasing standard error (greater confidence in the observed treatment effect). This figure gives rationale for including the data review region since it is probable that moderate observed treatment effects will not achieve success with a sample size of 30 per arm.

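### Optional sensitivity analysis 3 uses the upper credible limit of what is most plausibly an average change as a cut-off for individuals, so it could exclude roughly a quarter to a third of participants instead of a small tail

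*SAP*

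**What the plan says.** Sensitivity analysis 3 in SAP 7.1.5.1 is optional. It removes participants whose 26 h measurement "in the saline lobe increases by at least 40% relative to baseline" and refits the primary model to the rest. The source given for the threshold is: "This is the 95th percentile of the credible interval for 11 participants that underwent segmental LPS challenge over 2 periods". The SAP then reports the historical figure: "The median for 26 h BAL total protein in the saline lobe was 13.7"%, with a 95% credible interval of -8.8% to 40.4%. The stated reasons are that some participants may have received more LPS than intended, may be more sensitive to it, or may have had a more invasive lavage.

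Elsewhere in the same section the SAP says what a median with a credible interval means when results are presented: "Point estimates (median values of posterior distributions), the standard deviation of the posterior distribution (SDs) and 95% credible intervals (CrI"). These are summaries of a posterior distribution.

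Protocol 10.1 describes the same historical source as analysed "using a random effects model with total protein levels from 11 participants measured at baseline and 24 h over 2 study periods". For the LPS lobe it gives a log-scale mean whose estimate on that "scale is 5.47 (95% CI 5.23, 5.72"), and a variance whose estimate on that "scale is 0.25 (95% CI 0.13, 0.69").

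The documents give no expected number of exclusions.

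**The concern.** An interval for an average shows how well 11 people seen twice fix the typical saline-lobe change. It says little about how far one person's change may lie from that typical value, and it narrows as the historical sample grows while individual spread does not. If its upper limit is used as a threshold for individuals, many ordinary participants will exceed it.

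At stake is the usefulness of the check. A weaker posterior probability after exclusion might reflect only the smaller sample, and a shifted estimate might reflect selection. Neither would say much about spill-over or lavage technique. The selection variable is also measured 26 h after the first dose, when both doses have been given, so exclusions need not be balanced between arms.

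**Working it through.** **Inputs.** Cut-off +40%; historical change 13.7% (-8.8%, 40.4%) (SAP 7.1.5.1). 11 participants over 2 periods; LPS-lobe log mean 5.47 (5.23, 5.72); log variance 0.25, so SD 0.50; 30 per arm (Protocol 10.1).

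**1. Reproduce the plan's own figures.**
- Minimum observed effect for success at 30 per arm: 1 - exp(-1.645 × 0.50 × √(2/30)) = 19.1%. The protocol states 19%.
- Historical change on the log scale: ln 1.137 = 0.128, ln 0.912 = -0.092, ln 1.404 = 0.339.
- Half-width = (0.339 + 0.092)/2 = 0.216, so SE = 0.216/1.96 = 0.110.
- The 97.5th percentile of this posterior is exp(0.128 + 1.96 × 0.110) - 1 ≈ 41%, close to the stated 40.4%. The 95th is exp(0.128 + 1.645 × 0.110) - 1 ≈ 36%. The 40% is therefore the rounded upper limit of the interval.

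**2. Average or individuals?**
- In the same data, the confidence interval for the LPS-lobe mean has half-width (5.72 - 5.23)/2 = 0.245, beside an individual SD of 0.50. A half-width of 0.216 is the size of a mean's interval in this dataset.
- Read as individual spread, the interval implies a log SD of 0.11 for the ratio of two lavages from different segments (left lower lobe at 2 h, lingula at 26 h). With an assumed log SD of 0.3 to 0.5 per sample, that needs a within-person correlation of 1 - 0.11²/(2 × SD²), or 0.93 to 0.98.

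**3. Share excluded if the interval is for the average.** Individual SD = half-width/quantile × √n. Share = 1 - Φ[(ln 1.40 - ln 1.137)/SD] = 1 - Φ(0.208/SD).

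| Historical changes (n) | Individual log SD | Share at or above +40% | Of 60 |
|---|---|---|---|
| 11, t quantile (10 df) | 0.32 | 25.8% | 15.5 |
| 11, normal quantile | 0.365 | 28.4% | 17.1 |
| 16, normal quantile | 0.44 | 31.8% | 19.1 |
| 22, t quantile (21 df) | 0.49 | 33.4% | 20.1 |
| 22, normal quantile | 0.52 | 34.3% | 20.6 |
| Interval read as individual spread | 0.11 | 2.9% | 1.8 |

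The value 16 is the effective sample size implied by the LPS-lobe mean: (1.96 × 0.50/0.245)².

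**4. Sensitivity to the typical change.** Over SDs of 0.32 to 0.52, the share is 15-26% if the typical rise in this trial is 0%, and 31-38% if it is 20%.

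**5. Loss of precision.** Removing 26-34% leaves 22.2 to 19.8 per arm and multiplies the SE by 1/√0.74 = 1.16 to 1/√0.66 = 1.23. At variance 0.25 and a true 30% reduction, without baseline adjustment, the chance of meeting the 0.95 criterion is Φ[0.357/(0.50 × √(2/n)) - 1.645]. It falls from 87% at 30 per arm to 77-73%.

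**6. An individual 95th percentile.** exp(0.128 + 1.645 × SD) - 1 gives +93% (SD 0.32) to +166% (SD 0.52).

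**The case against.** The strongest objection is that nothing turns on this analysis. It may or may not be run, Table 2.4 is a conditional output for final reporting only, and the success and futility rules use the primary model alone. That stands: a reader might infer a threat to the primary conclusion, but the plan gives sensitivity analysis 3 no power to change it.

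Second, the SAP never calls the interval one for a mean, and the historical model is not shown. If its residual variance was pooled across conditions, the saline-lobe SD could be lower than derived here; at an assumed 0.20 the share is 1 - Φ(0.208/0.20), about 15%. The 0.50 comparator is also the SD of a level in another lobe, not of a within-person ratio. These points make the percentage conditional. They do not make 40% a sound individual percentile.

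Third, a reader might infer that the rule would remove more placebo than active participants. The order of events makes unequal exclusion possible, but the documents give no drug effect in the saline lobe from which to size it. The baseline is itself taken 2 h after the first dose, so an effect common to both samples cancels in the ratio. Protocol 5.4 expects blockade to leave unstimulated endothelium unaffected, although sensitivity analysis 1 allows for an effect by 2 h. Caution is justified; a figure for bias is not.

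Fourth, exclusions would not go unreported. SAP 12.7.2 requires them to be documented with reasons, and the shell used for Table 2.4 shows n by treatment.

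Finally, a strict cut-off can be a deliberate stress test. The SAP does not present it as one; it justifies 40% as a percentile.

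**Conclusion.** The point holds for an optional, supportive analysis. The cut-off is mislabelled (97.5th percentile, not 95th) and most plausibly comes from an interval for the average change. Under log-normal changes, 11 to 22 independent historical changes and a typical rise of 13.7%, it would exclude about 26-34% of participants, or 15 to 21 of 60. Allowing a typical rise of 0% to 20% widens this to about 15-38%. A true upper-tail percentile would exclude only a few per cent. The check would lose precision without singling out the participants it is meant to find. Any imbalance of exclusions between arms is of unknown size.

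**What to change.** Re-derive the total-protein cut-off as the intended upper percentile (for example the 95th, which is what the SAP names) of the posterior predictive distribution for an individual's saline-lobe/baseline ratio, using the same historical data. The +93% to +166% above is only a guide; the historical model should supply the value.

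Name total protein in the rule. It is written with the generic analyte placeholder, although 40% comes from total protein and the display list plans this analysis for total protein only. State that the analysis selects on a value measured 26 h after the first dose, after both doses, so exclusions may differ by arm.

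The alternative is to drop it and rely on sensitivity analysis 2, which does not exclude anyone for a high saline-lobe value, though it too uses the 26 h measurement.

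The cost is a few lines of SAP text and one re-run of the historical model. The drawback is that a higher threshold may miss partial spill-over: in the SAP's mock table the placebo LPS-lobe geometric mean rises from 93.81 to 248.80, about +165%, which is near the top of the indicative range.
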